# 6.3. Retests, Unscheduled Visits and Early Termination Data

For by visit analyses and summaries, efficacy, safety, HRQoL, and biomarker data (including scheduled, retests, unscheduled, and early termination) will be assigned to visits after the application of the windowing conventions described in Section 6.4. All measurements will be considered in summaries of abnormalities or worst-case values

Document: \quintiles.net\enterprise\Apps\sasdata\SASb\SAS\Arena\APD334\RZA28116\Biostatistics\Documenta

tion\SAP\503-Final SAP v2.0\APD334-203\_SAP\_Final v2.0-20231120\_clean.docx

Author: PPD Version Number: 2.0

Version Date: 20Nov2023

Template No.: CS TP BS016 Revision 7 Reference: CS WI BS005

Effective Date: 01Nov2021

Page 22 of 70

post-Baseline.

The visit windowing will be applied before missing data are imputed.

Listings will include scheduled, unscheduled, retest, and early termination data.

# 6.4. Windowing Conventions

All scheduled study visits are defined relative to Study Day 1, the date of first dose administration. Scheduled visit windows are defined in Clinical Study Protocol APD334-203 Appendix 1. A windowing convention will be used to determine the analysis visit value for a given measurement and will be applicable for all by-visit summaries and analyses for efficacy and safety data. Refer to Table 2 for specific visit windows.

For cardiac remonitoring upon treatment reinitiation after Day 2, as evidenced by more than 1 timed measurement in vital signs or electrocardiogram (ECG) parameters on the same collection date of an unscheduled visit, measurements will be mapped to analysis visit of Cardiac Remonitoring 1, Cardiac Remonitoring 2, etc. in the respective analysis dataset. For analysis, each timed measurement will be programmatically assigned to the nearest hourly timepoint (eg, Predose, 1-hour Postdose) based on their relationship to the dosing time on the same day. If the dosing date/time on the same day is missing, the timepoint will remain missing. Once mapped, these timed measurements from cardiac remonitoring visits will not be considered for any other analysis visit.

Windowing will be applied prior to any missing data calculations. The last non-missing measurement taken prior to Day 1 (including unscheduled assessments) will be labeled as "Baseline". Unless stated otherwise, data from all visits including scheduled, unscheduled and ET visits will be eligible for allocation to an analysis visit. The 2-Week and 4-Week Follow-Up visits will not be included in the visit windows and will be summarized separately without any window applied.

If one or more results for a variable are assigned to the same analysis visit, the result with the date closest to the protocol scheduled day will be used in the analysis, except for component subscores of MMS or TMS, in which case, the composite score and component subscores from the same date will be used in the analysis. If two measurements in the same analysis visit window are equidistant from the protocol scheduled study day, the earliest measurement will be used in the analysis. If multiple assessments are available on the same day, then the average of the assessment will be used in the analysis, except for laboratory and ECG data where the assessment at the earliest time of the same day will be used. If both central and local assessments of the same ECG or lab test are available on the same day/analysis visit, the central result will take precedence over the local result.

Document: \quintiles.net\enterprise\Apps\sasdata\SASb\SAS\Arena\APD334\RZA28116\Biostatistics\Documenta

tion\SAP\503-Final SAP v2.0\APD334-203\_SAP\_Final v2.0-20231120\_clean.docx

Author: PPD Version Number: 2.0

Version Date: 20Nov2023

Template No.: CS\_TP\_BS016 Revision 7 Reference: CS\_WI\_BS005

Effective Date: 01Nov2021

Page 23 of 70

For the overlapping visit windows at Week 12 and Week 8, a hierarchical algorithm will be applied as following: always map to the Week 12 study visit if the study day falls within the visit window of the Week 12 study visit, then assess the other records for the Week 8 study visit.

Table 2: Visit Windows for Efficacy and Safety Analyses

For All Efficacy (Except Endoscopy/MMS/Histology), Efficacy-Related Biomarkers, Safety Labs and Vital Signs			
Scheduled Study Visit (Protocol Scheduled Day)	Analysis Visit Window (Study Day)		
Baseline	≤1		
Week 0 (Day 1)	1		
Week 0 (Day 2)a	2		
Week 2 (Day 15 ± 3)	2 to 22, or 3 to 22a		
Week 4 (Day 29 ± 3)	23 to 43		
Week 8 (Day 57 ± 3)	44 to 71		
Week 12 (Day 85 ± 7)	> 71		
	gy/All Composite Endpoints That Include an Endoscopy Component sysician's Global Assessment, Health-Related Quality of Life, ECGs, OCT,		
Scheduled Study Visit (Protocol Scheduled Day)	Analysis Visit Window (Study Day)		
Baseline	≤1		
Week 0 (Day 1)	1		
Week 0 (Day 2)a	2		
Week 12 (Day 85 ± 7)b,c	66 to 113e (66 to 141 for assessments impacted by COVID-19 pandemic)d		
	or 57 to 113 f (57 to 141 for assessments impacted by COVID-19 pandemic) e		

a Applicable only for participants who required extended monitoring on Day 2 for vital signs and ECGs

Document: \quintiles.net\enterprise\Apps\sasdata\SASb\SAS\Arena\APD334\RZA28116\Biostatistics\Documenta

tion\SAP\503-Final SAP v2.0\APD334-203 SAP Final v2.0-20231120 clean.docx

Author: PPD Version Number: 2.0

Version Date: 20Nov2023

Template No.: CS\_TP\_BS016 Revision 7 Reference: CS\_WI\_BS005

Effective Date: 01Nov2021

<sup>b Applicable to all Week 12 efficacy endpoints based on any component of Mayo clinic score, such as clinical remission and symptomatic remission. Protocol visit window for PFT and OCT at Week 12 is Day  $85 \pm 7$  (FDA 2020)

c Due to overlapping windows at Week 12 and Week 8, a hierarchical algorithm will be used for the mapping. Week 12 will always be mapped first, then assess records for the Week 8 mapping. If scheduled Week 8 and 12 visits are both present in the same visit window, they will be mapped to separate visits (ie, Week 8 and Week 12)

d Assessments impacted by the COVID-19 pandemic are reported in the Date of Visit eCRF

Page 24 of 70

COVID-19, Coronavirus disease 2019; ECG, electrocardiogram; eCRF, electronic case report form; MMS, modified Mayo score; OCT, optical coherence tomography; PFT, pulmonary function test; RB, rectal bleeding; SF, stool frequency

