6.3.1. Instructions for Missed Dose(s)

Participants should be instructed that if they forget to take a dose, they can take the dose within 8 hours of the normal dosing time; otherwise, they should take their next dose at the regular time on

the following day. If the participant vomits the tablet, he/she should be instructed not to take another tablet on the same day, but to take the next dose at the regular time on the following day. Missed doses should be recorded in the participant's electronic diary (eDiary). Participants should be instructed to contact the Investigator if they miss more than 2 consecutive doses.

Participants must be educated to contact the Investigator to discuss treatment re-initiation if they do not take the study treatment for ≥ 2 consecutive days within the first week of treatment or for ≥ 7 consecutive days after the first week of treatment. \geq The participant must take the next dose of study treatment at the study site, and the in-clinic cardiac monitoring as outlined in Section 9.4.2.1 should be performed.

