9.4.2.1.4. Cardiac Monitoring Upon Treatment Re-Initiation Following Dose Interruption

Participants should undergo the same first dose cardiac monitoring procedures as the original treatment initiation when study treatment dosing is re-initiated after interruption for:

- ≥ 2 consecutive days within the first week of treatment
- ≥ 7 consecutive days after the first week of treatment

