9.9.2. Vital Signs

Resting vital signs measurements will be performed according to the Schedule of Assessments ([Table 6](#)) with the participant in the sitting position. Vital signs will be measured prior to any blood draws that occur at the same study visit.

Blood pressure may be measured manually or by automated device. Proper technique should be utilized during the measurement of BP to include the following:

- The participant's arm should be bare and supported at heart level.
- An appropriately sized cuff (cuff bladder encircling at least 80% of the arm) should be utilized. Participant's legs should not be crossed during the evaluation.

9.9.3. 12-Lead Electrocardiogram

All 12-lead ECGs will be performed according to Section [9.4.2.1](#) and the Schedule of Assessments ([Table 6](#)), and if clinically indicated at any time during the treatment period per Investigator discretion. All ECGs will be recorded from a 12-lead ECG machine with the participant in the supine position. Every attempt should be made to ensure the participant 12-lead ECG readings are obtained using the same machine throughout the study.

Intervals to be provided on the confirmed read for each safety 12-lead ECG are: RR, PR, QRS, QT, and QTcF. If an ECG shows a new onset QTc interval > 500 ms during the treatment period, a repeated ECG is warranted. If this abnormal finding is confirmed, study treatment must be interrupted. Effective diagnostic and therapeutic strategies should be employed.

Reversible causes of prolonged QTc interval (eg, electrolyte abnormalities or hypomagnesemia), should be corrected as clinically indicated. When evaluating a participant with new onset QTc interval above 500 ms, referral to a cardiologist experienced in treating cardiac conduction disorders should be considered. Re-initiation of study treatment (refer to Section [9.4.2.1](#)) can only be considered after all of the following have occurred:

- The QTcF interval is < 450 ms (men) or < 470 ms (women)
- The QTc prolongation is considered by the Investigator and confirmed by the cardiologist as not related to study treatment and likely caused by other factors
- Individual risk-benefit is favorable (as determined by the Investigator, in agreement with the cardiologist), **AND**
- After discussion with the Medical Monitor.

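### SAP 6.4 recognises cardiac re-monitoring by repeated readings at an unscheduled visit rather than by the dose restart, so a restart recorded under a scheduled visit is not mapped

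*SAP*

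**What the plan says.** The rule in SAP Section 6.4 begins by setting its scope: "For cardiac remonitoring upon treatment reinitiation after Day 2". It then says how such an occasion is found in the data: "as evidenced by more than 1 timed measurement in vital signs or electrocardiogram (ECG) parameters on the same collection date of an unscheduled visit". Each reading so found goes to an analysis visit called Cardiac Remonitoring 1, 2 and so on, and is given an hourly timepoint from the dosing time on that day. A missing dosing time does not stop the mapping: "If the dosing date/time on the same day is missing, the timepoint will remain missing". The mapping is exclusive: "Once mapped, these timed measurements from cardiac remonitoring visits will not be considered for any other analysis visit".

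Readings that are not mapped follow the general windowing rules of the same section. There, "If multiple assessments are available on the same day, then the average of the assessment will be used in the analysis", with an exception for laboratory and ECG data, for which the earliest reading of the day is taken.

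The protocol defines the occasion differently. Section 9.4.2.1.4 states: "Participants should undergo the same first dose cardiac monitoring procedures as the original treatment initiation when study treatment dosing is re-initiated after interruption for" at least 2 consecutive days in the first week, or at least 7 consecutive days after it. Section 6.3.2 gives the same two triggers. On the place of dosing, Section 6.3.1 says "The participant must take the next dose of study treatment at the study site" and specifies no type of visit.

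**The concern.** The SAP's test and the protocol's trigger are different things. The protocol's trigger is a dosing event. The SAP's test is a pattern of readings combined with a visit label, and it consults neither a dosing gap nor a dosing record. Dosing time enters only to label the hour.

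The mismatch can err in two directions. A real restart that happens to be recorded under a scheduled visit fails the unscheduled-visit condition. Repeated readings at an unscheduled visit for another reason, such as the adverse-event follow-up allowed in Protocol 9.6, can meet the condition without any restart.

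At stake are the displays meant to show what happens to heart rate when treatment is restarted. SAP 18.1.5 lists bradycardia and AV conduction delay among the events of special interest. SAP Table 4 has a combined heart-rate criterion for the 4-hour reading on Day 1, Day 2 or a remonitoring visit, and SAP 18.5 plans a listing for participants who were re-monitored.

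**Working it through.** The plan states no figure on this point, so the check compares the two rules and then works through the averaging consequence.

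**Step 1: the two rules applied to five situations.** The SAP flag needs a date after Day 2, an unscheduled visit and more than one timed reading. The protocol trigger needs a restart after a qualifying gap.

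| Situation | SAP flag | Restart? | Result |
|---|---|---|---|
| Restart at its own unscheduled visit | yes | yes | correct |
| Restart recorded under scheduled Week 4 (Day 29) | no | yes | missed |
| Two timed readings at an unscheduled adverse-event visit | yes, if the evidence clause is used alone | no | wrong label |
| Single repeat ECG at an unscheduled visit | no | no | correct |
| Repeat blood pressure at scheduled Week 8 | no | no | correct |

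The two errors come from the visit-type condition (second row) and from the absence of a restart check (third row).

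**Step 2: the visit value after a missed restart.** Vital signs are due at Weeks 2, 4 and 8 (Protocol Table 6), and first-dose monitoring adds readings at 1, 2, 3 and 4 hours (Protocol Table 2). That makes five heart rates on one day. If unmapped, they are averaged.

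The documents give no restart profile, so the following is an assumption: pre-dose 70 bpm, maximum post-dose fall *d*, and hourly readings 70 − 0.5*d*, 70 − *d*, 70 − *d*, 70 − 0.8*d*. The same-day average is (5 × 70 − 3.3*d*) / 5 = 70 − 0.66*d*.

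| *d* (bpm) | Readings | Average | Below pre-dose |
|---|---|---|---|
| 5 | 70, 67.5, 65, 65, 66 | 333.5 / 5 = 66.7 | 3.3 |
| 10 | 70, 65, 60, 60, 62 | 317 / 5 = 63.4 | 6.6 |
| 15 | 70, 62.5, 55, 55, 58 | 300.5 / 5 = 60.1 | 9.9 |

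The visits at which no restart occurs contribute a single routine reading, so the averaged value is not comparable with them.

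**Step 3: Table 4 and the listing.** The combined criterion requires a 4-hour reading below 50 bpm and a fall of more than 10 bpm from pre-dose. The 4-hour readings above are 66, 62 and 58, so none of these three profiles meets it. On this shape it would take 70 − 0.8*d* < 50, that is *d* > 25; a lower pre-dose rate needs a smaller fall. When a participant does meet the numbers on an unmapped restart day, the day does not carry the Cardiac Remonitoring label and the readings have no assigned hourly timepoint, so neither the combined criterion nor the re-monitoring listing clearly picks the participant up.

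**Step 4: ECG.** The averaging rule exempts ECGs. Table 2 also gives ECGs no analysis window between Day 2 and Day 66, so a mislabelled unscheduled ECG in that interval has no other visit to be removed from.

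**The case against.** The strongest reply is that the rule opens by confining itself to treatment re-initiation. Read as a whole, two blood pressures at an adverse-event visit are outside its scope, and the wrong label arises only if a programmer implements the evidence clause by itself. That stands as a limit. It does not remove the ambiguity, because the evidence clause is the only operational test given and mapping goes ahead without a dosing time.

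Second, the documents do not say how hourly readings taken on a scheduled day are entered. If they go on an unscheduled page, the rule catches them. That is possible, but capture of a restart should not depend on an unstated data-entry convention.

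Third, a reader might infer that restart bradycardia disappears from the report. It does not. SAP 6.3 keeps all measurements in abnormality and worst-case summaries and puts unscheduled and retest data in the listings, and Table 4 has separate criteria of below 50 and below 40 bpm that need no visit label. At most the combined 4-hour flag and the dedicated listing entry are lost. Nor do Table 4 and the listing say expressly that their remonitoring visit is the Section 6.4 label.

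Fourth, a reader might infer that the repeat ECG called for in Protocol 9.9.3 after a new QTc above 500 ms is swept into Cardiac Remonitoring. A single repeat at an unscheduled visit is one timed reading and does not meet the test; a repeat at a scheduled visit does not meet it either.

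Lastly, wrongly labelled vital signs will often change no by-visit value, because the reading nearest the scheduled day is used.

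**Conclusion.** The point holds in a limited form. SAP 6.4 uses a proxy for the dose restart, and on its wording a restart recorded under a scheduled Week 2, 4 or 8 visit is not mapped to Cardiac Remonitoring. For that participant the by-visit heart rate and blood pressure mix pre-dose and post-dose readings. Under the assumed profile the heart-rate value is 3.3 to 9.9 bpm below pre-dose; the profile is an illustration, not an estimate. The combined Table 4 criterion and the re-monitoring listing may omit the participant. The reverse error, labelling repeated readings without a restart, depends on how the clause is programmed.

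The documents give no frequency for restarts on scheduled days, so no proportion of participants affected can be stated. Worst-case and abnormality summaries and listings keep every reading, ECG visit values are not averaged, and no efficacy analysis is touched. The correction is worth making because a stated rule can produce a wrong visit value and is cheap to repair.

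**What to change.** Amend the paragraph in SAP 6.4 as follows, before unblinding:

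- Define Cardiac Remonitoring as the date of the first dose after a gap that meets the protocol's existing triggers (6.3.2, 9.4.2.1.4), whatever the visit type.
- Identify the gap from the Dosing Administration eCRF together with the eDiary missed-dose records. SAP Section 14 puts interruptions on that eCRF, but Protocol 6.3.1 has participants record missed doses in the eDiary, and the documents do not show that all of these reach the eCRF.
- Keep repeated timed readings as a cross-check, to find restarts absent from those records.
- Map that date's post-dose readings to Cardiac Remonitoring. Use the pre-dose reading both as the reference for the re-monitoring and as the scheduled visit's value; the exclusivity sentence must then be limited to the post-dose readings.
- Leave repeated readings without a restart at their own visits.
- State that the remonitoring visit in Table 4 and in the Section 18.5 listing is the one defined here.

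The cost is one SAP paragraph, a programming change and a reconciliation of two data sources. It implies no change to the clinical monitoring rule.

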16. APPENDICES

16.1. APPENDIX 1: SCHEDULE OF ASSESSMENTS

Table 6: Schedule of Assessments – Screening and Induction Treatment Period

Evaluation	Screening Period  28 to  1	12-Week Treatment Period					2-Week Follow-Up Visit ^b ± 3 Days	4-Week Follow-Up Visit ^b ± 3 Days
		W0/D1	W2/D15 ^a ± 3 Days	W4/D29 ^a ± 3 Days	W8/D57 ^a ± 3 Days	W12/D85 / Early Termination ^b ± 3 Days		
Informed consent	X							
Inclusion/exclusion criteria	X	X						
Demographics	X							
Medical and social history ^c	X							
Ulcerative colitis history	X							
Chest X-ray ^d	X							
Tuberculosis test ^e	X							
Tuberculosis questionnaire ^e	X	X	X	X	X	X	X	X
Virology screen (HIV, HBV, HCV) ^f	X							
Randomization		X						
eDiary instruction ^g	X							
eDiary review		X	X	X	X	X		
MMS ^h		X				X		
Stool frequency and rectal bleeding subscore ⁱ		X	X	X	X	X		
PGA for total Mayo Clinic score		X				X		
UC-PRO/SS, SF-36		X				X		
Adverse event assessment	X	X	X	X	X	X	X	X

Evaluation	Screening Period  28 to  1	12-Week Treatment Period					2-Week Follow-Up Visit ^b ± 3 Days	4-Week Follow-Up Visit ^b ± 3 Days
		W0/D1	W2/D15 ^a ± 3 Days	W4/D29 ^a ± 3 Days	W8/D57 ^a ± 3 Days	W12/D85 / Early Termination ^b ± 3 Days		
Vital signs ^{j,k}	X ^j	X ^{j,k}	X	X	X	X	X	X
12-lead ECG ^{l,m}	X ^l	X ^{l,m}				X		
Physical examination ⁿ	X	X	X	X	X	X	X	X
Extraintestinal manifestations ^o	X					X	X	X
Pulmonary function test ^p	X ^q					X ^q	X ^q	
Ophthalmoscopy with OCT ^r	X					X	X ^r	
Urine drug screen ^s	X							
Pregnancy test ^t	X	X		X	X	X		X
CBC with differential and platelets	X	X	X	X	X	X	X	X
TBNK	X	X	X	X	X	X	X	X
Laboratory tests including hs-CRP ^u	X	X	X	X	X	X	X	
Stool sample/fecal calprotectin ^v	X		X	X	X	X		
Flexible proctosigmoidoscopy/colonoscopy and biopsy ^w	X					X		
PK assessments ^x		X	X	X	X	X	X ^x	X ^x
Biomarkers blood sample ^y		X				X ^z		
Concomitant medications and procedures ^{aa}		X	X	X	X	X	X	X
Drug dispensation/accountability ^{bb}		X	X	X	X	X ^{bb}		
Study treatment administration ^{cc}		X – Once daily						

^a All visits beyond W0/D1 may be virtual/hybrid visits (Section 9.6).

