# 6. GENERAL CONSIDERATIONS

# 6.1. Reference Start Date and Study Day

Study Day will be calculated from the reference start date and will be used to show start/stop day of assessments and events. It will appear in listing where an assessment date or event date appears.

Reference start date is defined as the day of the first dose of study medication (Day 1 is the day of the first dose of study medication).

If the date of the event is on or after the reference date, then:

Study Day = (date of event - reference start date) + 1

If the date of the event is prior to the reference date, then:

Study Day = (date of event - reference start date)

In the situation where the event date is partial or missing, Study Day, and any corresponding durations will appear partial or missing in the listings.

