### 6.2. Baseline

Unless otherwise specified, baseline is defined as the last non-missing measurement taken prior to the first dose administration (including unscheduled assessments). If measurements include time (except for health-related quality of life [HRQoL] instruments), the date/time will be used to define Baseline. Otherwise, only dates will be compared. For HRQoL instruments, only the date will be used to derive Baseline. In the case where the last non-missing measurement and the date of first dose administration coincide and time is not collected, if the measurement was planned in the protocol to be done prior to the date of first dose, that measurement will be considered in defining Baseline.

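### One sentence in SAP 6.4 cuts Baseline off before Day 1, contradicting SAP 6.2, SAP Table 2 and the protocol's Day 1 pre-dose baseline

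*SAP*

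**What the plan says.** SAP 6.1 fixes the reference point: "Day 1 is the day of the first dose of study medication".

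SAP 6.2 gives the general rule, introduced as applying unless otherwise specified: "baseline is defined as the last non-missing measurement taken prior to the first dose administration". Date and time decide where a time is collected. There are two special provisions. For quality-of-life instruments, "For HRQoL instruments, only the date will be used to derive Baseline". For a value that falls on the first-dose date with no time recorded, the rule for counting it is: "if the measurement was planned in the protocol to be done prior to the date of first dose, that measurement will be considered in defining" (the quote stops one word short of the end of the sentence).

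SAP 6.4, on visit windows, says that what is labelled Baseline is "The last non-missing measurement taken prior to Day 1 (including unscheduled assessments"). It also sends the reader to Table 2 for the windows themselves. Both panels of Table 2 give the Baseline window as study day 1 or earlier, and the second panel names PGA and health-related quality of life.

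The protocol's Schedule of Assessments (Table 6) has the row "PGA for total Mayo Clinic score" marked at Week 0/Day 1 and Week 12/Early Termination only. The SF-36 has the same two visits. Protocol 9.4.2.1 and the Table 6 footnotes on vital signs and ECG treat the Day 1 pre-randomization reading as baseline.

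**The concern.** Baseline is a shared derivation, and two sections of the SAP state it differently. They disagree for every value taken on Day 1 before dosing: 6.2 keeps it and the 6.4 sentence drops it. Because 6.2 yields to anything specified elsewhere, and SAP 6.3 routes by-visit efficacy, safety, HRQoL and biomarker data through 6.4, a programmer could take the 6.4 sentence as the controlling rule. Measures with a Screening value would then change from an older reference value, and measures first collected on Day 1 would have no reference value at all.

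**Working it through.** There is no planned figure to reproduce. The check applies each rule to the pre-dose visits in Protocol Table 6.

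**Step 1. The rules as conditions on study day.** Day 1 is the first-dose date, so the 6.4 sentence means study day < 1. Table 2 means study day ≤ 1. Section 6.2 means before dosing, which includes Day 1 pre-dose values. Table 2 alone does not separate pre-dose from post-dose readings on Day 1, so 6.2 is still needed to finish the definition.

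**Step 2. Which value becomes Baseline.**

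| Assessment | Scheduled before dosing | 6.4 sentence | 6.2 with Table 2 |
|---|---|---|---|
| PGA | Day 1 | none | Day 1 (but see step 4) |
| SF-36 | Day 1 | none | Day 1 (but see step 4) |
| Vital signs | Screening, Day 1 | Screening | Day 1 |
| 12-lead ECG | Screening, Day 1 | Screening | Day 1 |
| CBC, including lymphocytes | Screening, Day 1 | Screening | Day 1 |
| Laboratory tests, including hs-CRP | Screening, Day 1 | Screening | Day 1 |
| Fecal calprotectin | Screening | Screening | Screening |
| Endoscopy, PFT, OCT | Screening | Screening | Screening |

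Screening runs from Day −28 to Day −1. By SAP 6.1 a pre-dose study day is the plain date difference, so a Screening value lies 1 to 28 days before Day 1. Protocol 9.3 allows Screening to be extended, so 28 is the scheduled limit and not a hard bound.

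**Step 3. What follows if the 6.4 sentence is programmed literally.**

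- *SF-36.* The ANCOVA in SAP 17 models change from baseline with baseline as covariate, on an mFAS that requires a baseline (SAP 5.5). On schedule, no participant would qualify.
- *PGA and TMS.* TMS includes PGA, so no baseline PGA means no baseline TMS. Clinical response by TMS (SAP 16) cannot be computed, the TMS subgroup split at 8 (SAP 8.5) cannot be formed, and the baseline PGA and TMS lines in SAP 11 would be blank.
- *Blood counts and hs-CRP.* The lymphocyte and hs-CRP models in SAP 16.4 would take both the change and the covariate from Screening.
- *Vital signs and ECG.* By-visit changes, including the QTcF increase criteria in SAP 18.4.1, would be measured from Screening. The separate Day 1 first-dose vital-sign summaries in SAP 18.5 use the pre-dose value from the eCRF and are not touched.

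**Step 4. Does pointing 6.4 at 6.2 suffice?** Not for untimed Day 1 values. For HRQoL, 6.2 ignores the time, so a clock reading cannot place an SF-36 before the dose. The same-day rule then asks whether the measurement was planned before the *date* of first dose. SF-36 and PGA are planned for that date. Protocol 6.3 has participants take the dose after all pre-dose assessments on visit days, so such an assessment precedes the dose but not its date. Read as strictly as the 6.4 sentence, the 6.2 rule does not clearly admit them either.

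**The case against.** The best answer is that the intended rule is plain. Section 6.4 itself refers to Table 2, whose Baseline row admits Day 1 in the panel that names PGA and HRQoL. The sentence is not marked as an exception to 6.2. SAP 17 says HRQoL is administered at Baseline and Week 12, SAP 11 plans to summarise baseline PGA and TMS, and SAP Table 4 equates pre-dose with Baseline. All of this stands. The consequences above follow only if one sentence is read alone.

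A reader might infer more than the documents support:

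- *That Section 6.4 as a whole removes all PGA and HRQoL baselines.* It does not, because Table 2 is part of 6.4.
- *That UC-PRO/SS loses its baseline for the same reason.* SAP 17.1.1 and Appendix 3 describe a daily diary scored as a weekly mean of at least four of seven days. If the diary runs before Day 1, a score exists even under the 6.4 sentence. If it is given once at Day 1, as Protocol Table 6 shows, one daily score cannot make a weekly score under any of the rules. That is a separate conflict between schedule and scoring.
- *That all TMS endpoints fail.* Clinical remission by TMS is an absolute score and uses no baseline value.
- *That the primary analysis set is compromised.* The modified Mayo score is evaluated at Day 1, but its diary and endoscopy inputs come from before Day 1, and SAP 16.1.1 takes a baseline subscore missing from the eCRF from the IRT. The documents do not show that this set would change.

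**Conclusion.** The contradiction is real and needs correcting. The 6.4 sentence is the outlier against SAP 6.2, SAP Table 2 and the protocol. Its effect, if followed literally, is no scheduled baseline for PGA and SF-36, and a Screening baseline in place of Day 1 pre-dose for vital signs, ECG, CBC and laboratory tests including hs-CRP. Fecal calprotectin, clinical remission by TMS and UC-PRO/SS are not affected by it.

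This assumes that assessments are made on the Table 6 schedule, with no unscheduled earlier PGA or SF-36, and that the program follows the sentence and not Table 2. Nothing in the documents shows that this happened, so it is not demonstrated data loss. The outputs that would lose a baseline altogether are exploratory, supportive or subgroup summaries, and the SAP tests no hypothesis (SAP 3.3 and 6.5). Severity: minor.

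**What to change.** Make two wording changes.

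1. In SAP 6.4, replace *prior to Day 1* with *prior to the first dose administration (Section 6.2)*.
2. In the SAP 6.2 same-day rule, make the condition that the measurement was planned before the *first dose*, not before the *date of first dose*, and state that the rule also applies to HRQoL instruments. Untimed PGA and SF-36 planned for Day 1 before dosing then count as Baseline.

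The second change is needed because the first alone points to a rule that does not clearly admit those two instruments. The cost is a few words in the SAP and a check that the baseline flag is programmed to match. No data collection changes. The UC-PRO/SS baseline week should be specified separately, as this edit does not settle it.
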